9.2.3. Treatment Phase

Subjects meeting eligibility criteria will be admitted to the CRU/EMU and be assessed for continued eligibility according to the procedures for CRU/EMU entry in the Schedule of Events – Procedures in CRU/EMU (Appendix 1B). Device training including study drug administration procedures will be conducted. Training may include subject use of a practice 'dummy' device that does not contain any active drug. Eligible subjects will be stratified for use of inducing vs. non-inducing AEDs and for the use of chronic daily benzodiazepines, and randomly assigned to a treatment arm and be hooked up with EEG recording electrodes which will remain in place for the duration of the study. It is required that a Staff Caregiver be present to provide 1:1 coverage with the subject while in the CRU/EMU to watch for signs of a seizure episode. After randomization and EEG electrode hook-up is complete, the study medication, assigned to the subject, will be removed from the pouch and dispensed to the Staff Caregiver until drug administration. At the onset of the predictable seizure event, the Staff Caregiver will activate the device and give to the subject if the subject is capable of self-administration or will assist in helping the subject to administer the drug. The Staff Caregiver will signal the onset of the seizure event on the video EEG, start the stopwatch and mark the occurrence of the seizure event on a seizure diary. At 2 minutes after study drug administration, the Staff Caregiver will record whether the seizure event has ceased or is still ongoing. The Staff Caregiver will observe the subject for the next 2 hours and record seizure activity on a seizure diary during this time period. After this the Staff Caregiver will continue observation throughout the 24 hours following blinded study medication administration. During the seizure episode period, study procedures will be conducted according to the schedule in the Schedule of Events – Procedures in

CRU/EMU (Appendix 1B). If over the course of 7 days there is no recordable seizure episode, the subject will be dismissed, after completing the Exit Procedures. Note that the procedures in the Schedule of Events for the treatment day are only conducted on the day there is a treatable seizure event and drug has been administered.

When multiple procedures are scheduled at the same time point, the VAS assessment should be performed first, immediately followed by the PK draw.

All *Staccato* doses will be administered as one puff from a single inhalation device by the subject with or without the assistance of the study Staff Caregiver. The exact time of administration and correct intake of the medication will be noted and recorded in the CRF.

Subjects should have minimal postural changes for the first 1.5 hours after administration of study drug.

This document cannot be used to support any marketing authorization application and any extensions/ variations thereof.

REDACTED COPY

10. DESCRIPTION OF STUDY TREATMENTS

10.1. Description of Treatments

After admission to the in-patient unit subjects will be stratified by use of inducing vs. non-inducing AEDs and for use of chronic daily benzodiazepines, and randomly assigned (1:1:1) to one of 2 doses of STAP-001 (1 mg or 2 mg) or *Staccato* placebo.

10.2. Study Drug Materials and Management

Please consult the Pharmacy Manual for a complete description of the study drug and requirements for storage, handling, dispensing, accountability, returns and destruction.

10.2.1. Physical Description of Study Drug

Study drug will include STAP-001 and matching *Staccato* placebo. Details regarding formulation and dosage are presented in [Table 1](#): Investigational Product

Table 1: Investigational Product

	Investigational Product (Staccato Alprazolam (STAP-001) or Staccato Placebo)
Product Name:	Staccato Alprazolam (STAP-001) or Matching Staccato placebo
Dosage Form:	Inhalation device
Dosage Strength of STAP-001	1 mg, 2 mg, or placebo, per device
Route of Administration	Oral inhalation
Physical Description	White to off-white plastic device

10.2.2. Study Drug Packaging, Labeling, and Storage

Study drug will be packaged inside a sealed foil pouch. Blinding of study medication will be done according to the randomization schedule and performed by an unblinded observer or vendor who shall not be involved in any other aspect of this study.

Detailed instructions for unblinding will be provided to the site in the event of an emergency and it is necessary to find out the study treatment assigned to an individual subject. If feasible, the Medical Monitor should be consulted before breaking the blind, and if this is not feasible, the medical monitor should be advised of the unblinding within 24 hours.

The label(s) for the investigational product and placebo will include sponsor name, address and telephone number, the protocol number, investigational product name, dosage form, storage conditions, and required caution statements and/or regulatory statements, as applicable. Additional information may be included on the label as applicable per local regulations.

Details of the packaging, labeling and dispensing instructions can be found in the Pharmacy Manual.

Adequate supplies of study drug will be provided to each site. Study drug should be stored in the original package between 15°C to 25°C (59°F to 77°F), as stated on the product label, in a secure, temperature-monitored, locked area, under the responsibility of the Investigator or other authorized individual until dispensed to the subjects.

10.2.3. Study Drug Preparation and Administration

Each product is packaged inside a sealed foil pouch. Removal of a pull-tab from the product activates it and renders it ready for use, as indicated by illumination of a green light. Successful dosing is signaled by the extinguishing of the green light.

10.2.4. Study Drug Return and Disposal

The Sponsor (or designee) will review with the Investigator and relevant site personnel the process for study treatment return, disposal, and/or destruction, including responsibilities for the site versus the Sponsor (or designee). Specific requirements for destruction or return are defined in the Pharmacy Manual.

10.2.5. Study Drug Accountability

To satisfy regulatory requirements regarding drug accountability, all study drug will be reconciled in full. The Investigator or designee must maintain accurate records of the receipt of study drug, including date received, lot number, amount received, condition of the package, and the disposition of study drug.

Current dispensing records will also be maintained, including the date and amount of medication dispensed to each individual subject. Returned study drug records will be maintained and final study drug reconciliation will also be recorded for each subject.

10.3. Concomitant Medications and Procedures

All medications, including over-the-counter therapies (e.g., vitamins, herbal, and nutritional supplements), taken at the time of the Screening Visit through the Follow-Up Visit will be recorded in the subject's source documentation and documented in the eCRF.

With the exception of acetaminophen or ibuprofen for pain, ongoing doses of oral contraceptives, and stable background AEDs, medications other than study drug are not allowed from 12 hours before entry into the CRU/EMU until the end of the Treatment Phase, unless medically required.

After screening, the doses of the background AEDs should be kept stable if possible. If dose changes are deemed necessary, continued study participation of the subject should be discussed with the Medical Monitor.

Any concomitant medications taken during the Treatment Phase (up to 24 h after study drug administration), including any medication taken for the treatment of adverse events, will be recorded on the appropriate CRF. Recording of the concomitant medication will include the medication name, indication, dose, route, frequency, and time.

If a seizure episode does not stop within 5 minutes, rescue medication may be administered at the discretion of the principal investigator per the protocol of the research unit. If seizure activity continues despite use of rescue medication, the standard treatment protocol of the institution should be applied as appropriate.

In case a subject experiences respiratory distress, an inhaled short-acting beta-agonist bronchodilator should be available for use under standard dosing conditions as needed. Any concomitant medication deemed necessary for the wellbeing of the subject may be given at the discretion of the Investigator. Use of medications that are prohibited per protocol will require subject withdrawal from the study.

This document cannot be used to support any marketing authorization application and any extensions or variations thereof.

REDACTED COPY

11. STUDY ASSESSMENTS DESCRIPTIONS

The schedule of assessments and procedures is presented in the Schedule of Events (Appendix 1A and 1B) and should be referenced for details regarding the collection of each assessment at each visit.

11.1. Demographic Characteristics and Medical History

Demographic characteristics (i.e., gender, race and ethnic origin, date of birth, and calculated body mass index) will be collected at the Screening Visit, and detailed on the eCRF.

Thorough medical history, including EEG and brain imaging (MRI/CT) findings within the last 5 years, history of seizures, seizure pattern, frequency and characteristics during the last 12 months. Current medications, and co-morbidities will be collected at the Screening Visit and reviewed and updated at entry into the CRU/EMU for the Treatment Phase. Epilepsy history and seizure documentation are collated and submitted to the Epilepsy Study Consortium Review Board for review.

11.2. Vital Signs, Weight, and Height

Vital signs will be measured after the subject has been in a supine or semi-supine position for at least 5 minutes and will include blood pressure, pulse rate, respiratory rate, and oral temperature as defined in the Schedule of Events.

Weight will be measured per institution standard of care. Subjects should wear light clothing and remove his/her shoes before weight is measured. Height will be measured per institution standard of care, after the subject has removed his/her shoes. Height will only be measured at the Screening Visit. Weight and vital signs will be measured at each study visit according to the Schedule of Events. Weight and height will be used to calculate the subject's body mass index at Screening. Weight and height will be converted as needed to kilograms and centimeters, respectively, prior to statistical analyses.

11.3. Physical and Neurological Examination

A complete physical examination will include an examination of all major organ systems, and will be performed as indicated in the Schedule of Events (Appendix 1A and Appendix 1B). A complete neurological examination will be performed as indicated in the Schedule of Events (Appendix 1A and Appendix 1B).

11.4. 12-Lead Electrocardiogram

Twelve-lead ECGs will be performed after the subject has rested in a supine or semi-supine position for at least 5 minutes. Individual parameters including heart rate, PR, QT, QTcF, QRS, and RR intervals will be collected. Repeat ECGs (if deemed necessary) should be performed at least 5 minutes apart. The Investigator should indicate review of the electrocardiogram reports throughout the study by signing and dating each report.

11.5. Seizure Assessment

11.5.1. Staff Caregiver Seizure Episode Recording

It is required that a Staff Caregiver be present to provide 1:1 coverage with the subject while in the CRU/EMU. At the onset of the predictable seizure episode, the Staff Caregiver will activate the device and give to the subject if the subject is capable of self-administration or will assist in helping the subject to administer the drug. The Staff Caregiver will signal the onset of the seizure episode on the video EEG, start a stopwatch and record the onset of the seizure episode. At 2 minutes after study drug administration, the Staff Caregiver will record whether the seizure episode has ceased or is still ongoing. The Staff Caregiver will observe the subject for the next 2 hours and record seizure activity on a seizure diary during this time period. After this the Staff Caregiver will continue observation throughout the 24 hours following drug administration.

11.5.2. Video Electroencephalogram (EEG)

A 19-21-channel recording system will be used with a bipolar derivation. The display montage will include T4-T6-O2-O1-T5-T3 and T4-P4-Pz-P3-T3, apart from 2x4 (8) frontal to occipital leads.

Subjects will be fitted with EEG electrodes according to the international 10-20 system upon reporting to the CRU/EMU. The EEG electrodes will remain in place for the duration of the stay in the CRU/EMU.

EEG data will be sent to a central reader and evaluated in a blinded fashion.

11.5.3. Seizure Episode Severity Assessment

At the 6 hour time point after dose administration the subject will assess the seizure episode just experienced in relation to previous seizures experienced by the subject using the assessment tool found in the Appendix 3.

11.6. Pharmacokinetic Sampling

Blood samples will be collected into evacuated K2 EDTA tubes, e.g., Vacutainer®, from each subject according to the times specified in the Schedule of Events – Procedures in CRU/EMU (Appendix 1B). An indwelling catheter inserted into the forearm, or direct venipuncture may be used during the blood sampling procedure.

The total volume of blood drawn from each subject during this study will be approximately 100 mL, which includes approximately 24 mL for pharmacokinetic analysis and approximately 70 mL for standard pre-study and post study clinical laboratory tests.

Specific sample collection, preparation and shipping instructions will be provided to the study site. Samples will be assayed using validated methods. Instructions for harvesting and preparing plasma samples prior to freezing and additional procedures for blood sample collection will be provided in separate study laboratory manual.

11.7. Sedation Assessment - Visual Analog Scale (VAS)

The visual analog scale is a distinct 100 millimeter line anchored on the left end at full degree of impairment and on the right end at no degree of impairment, where indication of the degree of impairment perceived at the time of assessment is captured by marking the appropriate position

on the line between the anchor points. The measured distance of the mark from the left anchor will be recorded in millimeters

As specified in the Schedule of Events – Procedures in CRU/EMU (Appendix 1B), sedation will be measured using a 100-mm linear visual analogue scale (VAS). The subject will be given 2 scales, 1 anchored by “Sedated” and “Alert, the other by “Sleepy and “Awake” and asked to “Place a vertical mark on the line indicating your feelings RIGHT NOW”. The location of the mark will be measured at a later time and the results will be recorded in mm from the left on the appropriate eCRF.

An example of the subject VAS is provided in Appendix 2. The paper scales will be provided to the sites and only originals can be used for subject assessment. Photocopies cannot be provided for subject assessment.

11.8. Clinical Laboratory Assessments

Blood and urine samples will be collected according to standard medical guidelines and processed at a clinical laboratory. Sample collections, handling and shipping instructions are provided in the clinical laboratory document. Study-related clinical laboratory assessments are presented below in [Table 2: Clinical Laboratory Assessments](#)

Clinical laboratory samples should be collected according to the Schedule of Events -Procedures in CRU/EMU (Appendix 1B).

The results of clinical laboratory tests conducted at the Screening Visit (and prior to dosing) must be assessed by the Investigator to determine each subject’s eligibility for participation in the study. Laboratory values that are out of range at screening may be repeated at the investigator’s discretion. The Investigator should indicate review of the laboratory reports throughout the study by signing and dating each report.

Following study drug administration, all clinical laboratory results that fall outside the reference range will be interpreted by the Investigator as Abnormal, not clinically significant, or Abnormal, clinically significant. Laboratory results deemed Abnormal, clinically significant should be fully investigated and repeated for verification. Additional tests and evaluations required to establish the significance or etiology of a clinically significant abnormal result or to monitor the course of an adverse event should be obtained when clinically indicated. All clinically significant out-of-range laboratory values will be followed until they return to normal or stabilize; the investigator will treat the subject as medically required at appropriate intervals until this occurs.

Any significant laboratory abnormalities that are either serious or unexpected will be promptly reported to the Sponsor. Any additional relevant laboratory results obtained by the Investigator during the course of this study will be reported to the Sponsor or designee.

Laboratory values will be reported as an adverse event following the guidelines in section 12.1.1.

Table 2: Clinical Laboratory Assessments

Hematology (Blood)	Chemistry (Serum)	Pregnancy Females of childbearing potential only
Complete blood count Platelet count White blood cell count with differential Hemoglobin Hematocrit	Alanine aminotransaminase Albumin Alkaline phosphatase Amylase Aspartate aminotransaminase Total bilirubin Direct bilirubin Indirect bilirubin	At screening: Urine Human Chorionic Gonadotropin At CRU/EMU entry: Urine Human Chorionic Gonadotropin
Drug Screen (Urine)	Blood urea nitrogen Calcium Carbon dioxide Chloride Creatinine Creatine kinase Glucose Lipase Total protein Phosphorus Potassium Sodium Uric Acid	Urinalysis
delta-9-tetrahydrocannabinol barbiturates opioids amphetamines methamphetamines methylenedioxyamphetamine cocaine phencyclidine ethanol propoxyphene		Bilirubin Blood Clarity Urobilirubin Glucose, Urine Ketones Leukocyte Esterase Nitrate pH Protein, Urine Specific Gravity

12. ADVERSE EVENTS

12.1.1. Definition of Adverse Event

An adverse event is any untoward medical occurrence that may appear or worsen in a subject during the course of a study. It may be a new intercurrent illness, a worsening concomitant illness, an injury, or any concomitant impairment of the subject's health, including laboratory test values, regardless of etiology. Any worsening (ie, any clinically significant adverse change in the frequency or intensity of a pre-existing condition) should be considered an adverse event. A diagnosis or syndrome should be recorded on the adverse event page of the eCRF rather than the individual signs or symptoms of the diagnosis or syndrome. A worsening of the condition under study will not be reported as an adverse event.

All subjects will be monitored for adverse events during the study. Assessments may include monitoring of the following parameters: the subject's clinical symptoms, laboratory, physical examination findings, or findings from other tests and/or procedures.

An adverse event reported after informed consent and occurring before the first dose of study drug in the CRU/EMU, will be considered a pretreatment adverse event and will be captured on the eCRF. Adverse events will be considered treatment-emergent if the onset is after the first dose of study drug.

An abnormal laboratory value is considered to be an adverse event or a component of an adverse event if the abnormality:

- results in discontinuation from the study;
- is judged by the Investigator to be of significant clinical importance requiring treatment, modification/interruption of investigational product dose, or any other therapeutic intervention

Regardless of severity grade, only laboratory abnormalities that fulfill a seriousness criterion need to be documented as a serious adverse event.

If a laboratory abnormality is one component of a diagnosis or syndrome, then only the diagnosis or syndrome should be recorded on the adverse event eCRF. If the abnormality was not a part of a diagnosis or syndrome, then the laboratory abnormality should be recorded as the adverse event. If possible, the laboratory abnormality should be recorded as a medical term and not simply as an abnormal laboratory result (e.g., record thrombocytopenia rather than decreased platelets).

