6. STUDY OBJECTIVES

The overall objectives of the study are to assess the efficacy and safety of a single administration of STAP-001 in subjects with epilepsy with a predictable seizure pattern.

The primary objectives are:

- To assess the efficacy of STAP-001 (1.0 mg and 2.0 mg) compared to placebo in treating a seizure episode
- To assess the clinical feasibility and safety of the inhalation of STAP-001 (1.0 mg and 2.0 mg) compared to placebo in subjects during a seizure episode
- To assess the sedation associated with administration of STAP-001 (1.0 mg and 2.0 mg) compared to placebo

This document cannot be used to support any marketing authorization application and any extensions or variations thereof.

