12.1.2.1. Serious Adverse Event

A serious adverse event is an adverse event, as per Title 21 CFR 312.32 and ICH E2A.II.B that fulfills the following criteria:

- Is fatal (results in death);
- Is life-threatening (Note: the term "life-threatening" refers to an event in which the subject was at risk of death at the time of the event; it does not refer to an event that could hypothetically have caused death had it been more severe);
- Requires inpatient hospitalization or prolongation of existing hospitalization (hospitalization is defined as an inpatient admission, regardless of length of stay);
- Results in persistent or significant disability/incapacity (a substantial disruption of the subject's ability to conduct normal life functions);
- Is a congenital anomaly/birth defect; or
- Constitutes an important medical event that may jeopardize the subject or may require medical or surgical intervention to prevent one of the other outcomes listed above.

Important medical events are defined as those occurrences that may not be immediately life-threatening or result in death, hospitalization, or disability, but may jeopardize the subject or require medical or surgical intervention to prevent one of the other outcomes listed above. Examples of such medical events include allergic bronchospasm requiring intensive treatment in an emergency room or at home, blood dyscrasias or convulsions that do not result in inpatient hospitalization.

Events **not considered** to be serious adverse events are hospitalizations for:

- A procedure for protocol/disease-related investigations (e.g., sampling for laboratory, pharmacokinetic, and pharmacodynamic tests). However, hospitalization or prolonged hospitalization for a complication of such procedures remains a reportable serious adverse event.
- Hospitalization or prolongation of hospitalization for technical, practical, or social reasons, in absence of an adverse event.
- A procedure that is planned (i.e., planned prior to the starting of treatment on study); must be documented in the source document and the eCRF. Hospitalization or prolonged hospitalization for a complication remains a reportable serious adverse event.
- An elective treatment of or an elective procedure for a pre-existing medical condition that does not worsen.
- Emergency outpatient treatment or observation that does not result in admission, unless fulfilling other seriousness criteria above.

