12.1.6.1. Reporting Serious Adverse Events

The Investigator is required to notify the Sponsor, and the Sponsor's designated Drug Safety Unit within 24 hours after becoming aware of the occurrence of a serious adverse event. All serious adverse events will be reported through completion of the adverse event eCRF. The Investigator will be responsible for reporting serious adverse events to the IRB.

Medical Monitor:

[REDACTED]

Address:

Phone:

Email: [REDACTED]

Emergency (24/7) Contact Information:

site specific phone tree to be provided

Serious Adverse Event Reporting Contact Information:

[contact]

ions thereof.

If an Investigator becomes aware of a serious adverse event within 14 days after the last dose of study drug and it is considered by him/her to be caused by the study drug with a reasonable possibility, the event must be documented and reported through completion of the adverse event eCRF.

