Cardio-Respiratory		
Nasal Congestion	17.4	16.5
Tachycardia	15.4	26.8
Chest Pain	10.6	18.1
Hyperventilation	9.7	14.5
Upper Respiratory Infection	4.3	3.7
Sensory		
Blurred Vision	21.0	21.4
Tinnitus	6.6	10.4
Musculoskeletal		
Muscular Cramps	2.4	2.4
Muscle Stiffness	2.2	3.3
Cutaneous		
Sweating	15.1	23.5
Rash	10.8	8.1
Other		
Increased Appetite	32.7	22.8
Decreased Appetite	27.8	24.1
Weight Gain	27.2	17.9
Weight Loss	22.6	16.5
Micturition Difficulties	12.2	8.6
Menstrual Disorders	10.4	8.7
Sexual Dysfunction	7.4	3.7
Edema	4.9	5.6
Incontinence	1.5	0.6
Infection	1.3	1.7

* Events reported by 1% or more of XANAX patients are included.

In addition to the relatively common (ie, greater than 1%) untoward events enumerated in the table above, the following adverse events have been reported in association with the use of XANAX: seizures, hallucinations, depersonalization, taste alterations, diplopia, elevated bilirubin, elevated hepatic enzymes, and jaundice.

Panic disorder has been associated with primary and secondary major depressive disorders and increased reports of suicide among untreated patients (see **PRECAUTIONS, General**).

Adverse Events Reported as Reasons for Discontinuation in Treatment of Panic Disorder in Placebo-Controlled Trials

In a larger database comprised of both controlled and uncontrolled studies in which 641 patients received XANAX, discontinuation-emergent symptoms which occurred at a rate of over 5% in patients treated with XANAX and at a greater rate than the placebo treated group were as follows:

DISCONTINUATION-EMERGENT SYMPTOM INCIDENCE

Percentage of 641 XANAX-Treated Panic Disorder Patients Reporting Events			
Body System/Event			
Neurologic		Gastrointestinal	
Insomnia	29.5	Nausea/Vomiting	16.5
Light-headedness	19.3	Diarrhea	13.6
Abnormal involuntary movement	17.3	Decreased salivation	10.6
Headache	17.0	Metabolic-Nutritional	
Muscular twitching	6.9	Weight loss	13.3

Percentage of 641 XANAX-Treated Panic Disorder Patients Reporting Events

Body System/Event

Impaired coordination	6.6	Decreased appetite	12.8
Muscle tone disorders	5.9		
Weakness	5.8	Dermatological	
Psychiatric		Sweating	14.4
Anxiety	19.2		
Fatigue and Tiredness	18.4	Cardiovascular	
Irritability	10.5	Tachycardia	12.2
Cognitive disorder	10.3		
Memory impairment	5.5	Special Senses	
Depression	5.1	Blurred vision	10.0
Confusional state	5.0		

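### Section 12.1.1 excludes worsening epilepsy from adverse event reporting without exception, so serious seizure worsening after dosing can miss the AE and SAE data

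*Protocol*

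**What the plan says.** Protocol section 12.1.1 sets a general rule: "Any worsening (ie, any clinically significant adverse change in the frequency or intensity of a pre-existing condition) should be considered an adverse event". The same paragraph ends with an exclusion: "A worsening of the condition under study will not be reported as an adverse event". Section 6 identifies the condition; the study is "in subjects with epilepsy with a predictable seizure pattern".

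Section 12.1.2.1 builds the serious category on the AE definition: "A serious adverse event is an adverse event, as per Title 21 CFR 312.32". Its examples of important medical events include "blood dyscrasias or convulsions that do not result in inpatient hospitalization". Section 12.1.6.1 requires notification within 24 hours and gives one data route: "All serious adverse events will be reported through completion of the adverse event eCRF".

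Safety compared with placebo is among the primary objectives (section 6), and adverse events come first among the safety measures (section 13.2.3). SAP sections 3.3.3 and 3.6 define treatment-emergent events from recorded AEs. SAP section 3.7 declares no change to the protocol's analyses.

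**The concern.** Every subject has epilepsy, so on its face the exclusion covers status epilepticus, a prolonged seizure, or a clear rise in seizure frequency after dosing. It does so even when the event is life-threatening or the investigator suspects the drug. Because an SAE must first be an AE, the exclusion carries through to SAE reporting.

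At stake is the AE and SAE comparison that serves a primary objective, and the sponsor's prompt knowledge of serious seizure events. Section 7.3 also says that tolerability and safety in chronic benzodiazepine users are to be evaluated, and the same gap applies to them.

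**Working it through.** The plan states no figure on this point, so there is none to reproduce. The check is mainly a reading of the passages together.

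**1. Reach of the exclusion.** Section 12.1.1 attaches no condition on seriousness, causality, duration or seizure type. No carve-out appears elsewhere in the protocol or in the SAP.

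**2. The general rule.** The two sentences in 12.1.1 can be read together as a rule on pre-existing conditions followed by an exception for the studied condition. That removes the contradiction inside the paragraph. It does not limit the exception.

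**3. Serious events.** An event that is not an AE fails the opening words of the SAE definition in 12.1.2.1, and the AE eCRF is the only SAE form. The same section's convulsions example points the other way. A site treating a post-dose convulsion has one passage supporting an SAE report and another supporting no report.

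**4. Status epilepticus.** Exclusion criterion 2 in section 8.2 bars a history of it in the 6 months before Screening. An episode after dosing would be a departure from the subject's recent course, yet no passage says it is outside the exclusion.

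**5. What is recorded elsewhere.**

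| Source | What it captures | What it lacks |
|---|---|---|
| Primary endpoint (13.2.1) | Cessation by 2 min, recurrence to 2 h | Seriousness, causality |
| Rescue use (13.2.1) | Whether rescue was given | Same |
| Severity scale at 6 h (11.5.3, Appendix 3) | Comparison with the subject's typical episode, down to much worse | Same |
| Generalization flag (SAP 3.6) | Seizure type | Same; no reference to habitual type |
| Counts to 12 h, time to next seizure (SAP 3.6) | Number and timing | Same |
| Staff diary, 24 h observation, video EEG (11.5.1, 11.5.2, Appendix 1B) | Seizure activity to exit | Same |
| Concomitant medications to follow-up (10.3); injuries as AEs (12.1.1) | Indirect trace after exit | Seizures themselves |

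No row has status epilepticus as a category.

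**6. Length of the post-exit gap.** Exit is 24 to 32 h after dosing, or 1.00 to 1.33 days. The call is at 14 ±2 days, or 12 to 16 days.
- Shortest gap: 12 − 1.33 = 10.67 days.
- Longest gap: 16 − 1.00 = 15 days.

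At the qualifying minimum of 4 episodes per 28 days, the expected episodes are 10.67 × 4/28 = 1.5 to 15 × 4/28 = 2.1. These are habitual seizures at the entry rate. They show the background against which worsening would have to be recognised, not a rate of harm.

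**7. Reading an empty AE table.** Part 2 plans 2 × 35 = 70 evaluable subjects on active drug; the 8 from Part 1 make 78. With zero recorded events, the one-sided 95% upper bound is 1 − 0.05^(1/n).
- n = 70: 4.2%.
- n = 78: 3.8%.

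For seizure worsening, such a bound has no meaning if the events were excluded by rule.

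**The case against.** The strongest reply is that worsening around dosing is measured closely and compared by arm. The subject is watched one-to-one with continuous video EEG read centrally and blind, and the SAP plans a listing of post-treatment seizures (Listing 16.8.6). That stands. A reader might infer that these events vanish from the trial, and the documents do not support that.

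Nor is there nothing after exit. Medications are recorded through follow-up, and an injury is expressly an AE. Section 12.1.6.2 requires immediate contact about urgent safety issues, and section 14.3 has the investigator inform the IRB/EC of events affecting subject safety. These routes weaken any claim that the sponsor would not hear of a serious event. They do not place it in the AE or SAE data.

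Scope is also open. Section 12.1.1 asks sites to record a diagnosis or syndrome, so a site might enter status epilepticus or a new seizure type as a new diagnosis. This is a fair point, strongest for a new seizure type. It also means capture would depend on each site's reading.

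The appended label (Appendix 4) lists "seizures, hallucinations, depersonalization, taste alterations, diplopia" among events reported with alprazolam. It would be tempting to read this as an expected harm of the study dose. The list follows the panic-disorder table, and the label's account of attributable seizures concerns stopping or reducing repeated oral dosing. It gives no rate for one inhaled dose. With the 11-hour half-life in section 13.4.3, five half-lives take 5 × 11 = 55 h, so most of the post-exit window falls after substantial elimination.

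**Conclusion.** The concern holds for classification and reporting. As written, status epilepticus or prolonged, more frequent or serious seizures after dosing can be left out of the AE and SAE tables, with no seriousness or causality assessment and no 24-hour SAE report. The convulsions example makes inconsistent reporting between sites possible; the documents do not show that it occurred. Direct seizure recording also lapses for about 10.7 to 15 days before the call.

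The size in events cannot be derived, because the documents give no rate of seizure worsening on drug or placebo. A reader might take the 1.5 to 2.1 episodes expected after exit as evidence that worsening is likely. They are habitual seizures and do not show that. The primary efficacy result is unaffected.

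The conclusion assumes that sites read worsening of the studied condition to include status epilepticus and prolonged or more frequent seizures. For a new seizure type the term is undefined, and that part of the point is weaker.

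**What to change.** Reconcile sections 12.1.1, 12.1.2.1 and 12.1.6.1 by replacing the last sentence of the first paragraph of 12.1.1 with wording such as:

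> Seizures consistent in type, duration and frequency with the subject's history and qualification diary are efficacy data and are not AEs. Status epilepticus, a clinically significant increase in seizure frequency, duration or intensity, a new seizure type, and any seizure meeting a seriousness criterion are reported as an AE or SAE.

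Ask about these events at the existing day-14 call. No post-exit diary is added, so frequency after exit would rest on recall.

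The cost is more than a site memo. Section 14.4 requires a protocol amendment, with IRB/EC approval before implementation unless it is administrative, at approximately 50 sites. Some additional AE reports will reflect natural course; these should be expected in all arms, placebo included.
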